# 5.1.2 Plans to promote retention

To minimise attrition, we will use multiple methods to keep in contact with patients. We will ask patients for full contact details (including mobile phone number and email address). Patients will also be asked to consent to agree to their General Practitioner being contacted for their address and using NHS Digital (the Spine portal) to help stay in contact in England and Wales or the Community Health Index in Scotland. For all follow-up data collections, two reminders (at 2 weeks and 4 weeks) will be sent to non-responding participants, with a final attempt to obtain data by a telephone/video call at 6 weeks. Around a month before the 12 month questionnaire is due (primary end-point), the participant will receive by post/electronically a flyer to expect the questionnaire as there is evidence that prenotification can improve response rates.(44) Participants will receive a gift voucher for completing questionnaires at 6 weeks (£5), 3 months (£5), 6 months (£20) and 12 months (£20).(44) The increase at 6 months is because the data collection is not aligned to a clinic and at 12 months as this is the primary end-point. We will text participants to prompt completion as part of the embedded SWAT and non-responders will be contacted via text, email or mobile when necessary about being available to complete the questionnaire over the telephone or video.(44) Regular newsletters will be sent to participants during the trial to keep them informed and engaged with the trial.(45) In addition, we will underpin data collection based on our experience and stakeholder engagement when completing another

orthopaedic surgical RCT in a primarily young, male population (SWIFFT HTA – 11/36/37).(46, 47)

Imaging and reports from peripheral sites can be directly accessed by the participating site to help with assessment of bone union, imaging can also be retrieved by the participating hospital for local area/regional hospitals using Picture Archiving Communication Systems (PACS). Furthermore, if a participant moves away from the participating site and is followedup at a hospital not taking part in the trial, follow-up data (e.g. re-operations, complications, infections) can be requested securely through NHSmail. Both these mechanisms for capturing data are available as would occur in routine clinical practice. A bespoke letter and flyer is also available to hospital staff to encourage participant attendance at the 12 month clinic which is the primary end-point for the study.

## 5.2 Proposed time period for retention of relevant trial documentation

Essential Trial documentation (i.e. the documents which individually and collectively permit evaluation of the conduct of a clinical trial) will be kept with the Trial Master File and Investigator Site Files. The sponsor will ensure that this documentation will be retained for a minimum of five years after the conclusion of the trial to comply with standards of GCP. They will then be securely destroyed as per York Trial Unit Standard Operating Procedures and/or that of the Sponsor.

Data that is collected on paper will be stored for a minimum of 10 years after the conclusion of the trial in a secure University managed storage facility or off-site and similarly then destroyed securely. Data that is stored electronically will also be stored for a minimum of 10 years on secure, password-protected University computers. We plan to indefinitely store deidentified data, with the unique study ID removed, that is truly anonymous.

# 5.3 Embedded Study Within A Trial (SWAT)

An electronic prompt compared with no prompts may improve patient follow-up (RR 1.03 (0.98 to 1.08)).(44)

An embedded SWAT, not yet being undertaken from a search of the Northern Ireland SWAT repository, will be conducted to evaluate whether including a timeframe to complete the questionnaire has an effect on questionnaire return. Participants will be randomly allocated on a 1:1 ratio to get a prompt at each follow-up that either will or will not ask for the questionnaire to be completed within the next 7 days. Our PAG has informed the wording of the text message.

Generation of the SWAT allocation will be undertaken independently by a statistician at York Trials Unit not involved with the DIDACT follow-up process. Block randomisation stratified by the main trial treatment allocation using randomly permuted block sizes will be used. Allocation will take place at the time of allocation to the main trial. The sending of text messages will be hosted outside of REDCap and will be sent using a secure UK-based text message gateway software, for example, Intelli Software.

The primary outcome of this embedded SWAT is the response rate to the participant followup questionnaire at 12 months. Secondary outcomes include: response rates to the participant follow-up questionnaire at 6 weeks, 3 months and 6 months; whether the participant required a reminder; completeness of the primary outcome for the main trial (defined as providing sufficient data to produce a valid summary score); and time to response. Analysis of dichotomous outcomes will be via a mixed-effect logistic regression model adjusting for main trial allocation, and site as a random effect. Time to response will be analysed using a Cox proportional hazard model with shared centre frailty and adjusting for main trial allocation.

# 6 Statistical methods

## 6.1 Internal pilot

The recruitment rate and 95% confidence interval (CI) will be estimated from the data collected. A CONSORT diagram will be constructed to show the flow of participants through the study and the following outcomes calculated: number of eligible patients; proportion of eligible patients approached for consent; proportion of eligible patients not approached and reasons why; proportion of patients approached who provide consent; proportion of patients approached who do not provide consent; proportion of patients providing consent who are randomised; proportion of patients randomised who do not receive the randomly allocated treatment; proportion of patients dropping out between randomisation and follow-up; proportion of patients for whom a primary outcome is recorded. Data will be summarised on the reasons why eligible patients were not approached, reasons for patients declining to participate in the study; reasons why randomised patients did not receive their allocated treatment and reasons for drop-out, if available. Results will be compared against the study's recruitment assumptions and progression targets.

# 6.2 Statistical analysis full trial

For the analysis of the full trial (assuming continuation) a CONSORT flow diagram will be provided to display the flow of participants through the study. Baseline characteristics will be presented descriptively by group. All outcomes will be reported descriptively at all collected time points. Continuous data will be presented using means and standard deviations or medians and ranges as appropriate, and categorical data will be presented using frequencies and percentages. The primary analysis will be on an intention-to-treat (ITT) basis, analysing patients in the groups to which they were randomised. A mixed-effects linear regression model will be used to compare groups, adjusting for stratification factors and relevant baseline covariates as fixed effects and centre as a random effect. Non-inferiority will be accepted if the upper bound of the two-sided 95% confidence interval (equivalent to a one-sided 97.5% CI) lies within the non-inferiority margin of 10 at the 12 month time point.

Completeness of data at follow-up will be reported by group. In non-inferiority comparisons in the presence of treatment switching the ITT analysis could bias towards the null, which may lead to false claims of non-inferiority, hence we will undertake both ITT and CACE (complier average causal effect) analyses. Full analyses will be detailed in the trial's statistical analysis plan (SAP), which will be reviewed and approved by the trial steering and data monitoring committees and finalised before the end of patient follow-up. All analyses will be conducted in STATA v17 (StataCorp LP, College Station, TX, USA), or later (to be confirmed in the final report).(48)

# 7 Economic analysis

The embedded health economic evaluation assesses the relative cost-effectiveness of surgery compared with sling immobilisation in the management of adults with a displaced fracture of the distal clavicle in order to determine which treatment offers the best value for

money for the NHS. The methods will be consistent with the NICE Guide to the Methods of Technology Appraisal.(49)

An NHS and personal social services (PSS) costing perspective will be taken in the base case analysis; relevant costs will include participant level NHS resource use, medication use and related social services. The time horizon of the analysis will be 12 months. A secondary analysis will explore the wider societal perspective.

The costs of providing the treatments will be based on national tariff data. Applying national average costs makes the results more generalisable when cost-effectiveness results are considered for wider adoption by policy-makers. We will also include the cost of the operation to remove metalwork implanted in the surgery arm and the necessary surgery following non-union in the sling immobilisation arm. These costs represent key extra costs of the respective treatment arm and are an important resource implication which is factored into the economic evaluation.

Health care utilisation data for contacts with the NHS and PSS are recorded using a bespoke service use questionnaire. The healthcare resource data will be collected using patient self-administered questionnaires and hospital forms. Quantities recorded are multiplied by national average unit costs in the appropriate year at the time of analysis (50, 51) to derive a cost profile for each participant in each arm of the trial.

We will also collect costing data to inform a cost-utility analyses from a societal perspective. The trial will assess the impact of both treatments on days of lost employment by participants and their unpaid carers, and any paid additional care required. In addition to the base-case analysis conducted from the perspective of the NHS and PSS, we will conduct a secondary analysis to explore the impact of productivity costs and extra personal spending on cost effectiveness results. The wider cost data does not form part of the base case but can be submitted as supplementary evidence.

Health related quality of life (HRQoL) will be quantified using EQ-5D-5L(52) administered at baseline, six weeks, 3, 6 and 12 months. The UK social tariff is applied to EQ-5D-5L responses to derive utility values from patient responses at each data point. We will use the valuation method as recommended by NICE at the time of analysis to calculate Quality Adjusted Life Years (QALYs)(53) using the area under the curve approach.(54) QALYs will be the primary outcome for the economic evaluation.

Regression methods, adjusted for key covariates, will be used to estimate incremental costs and QALYs (on an ITT basis) by treatment allocation. Patient costs are combined with QALYs to estimate the incremental cost per QALY of the surgery comparing to the sling immobilisation over the follow-up.

If deemed appropriate the short-term cost-effectiveness will be extrapolated beyond the trial follow-up.

Underlying uncertainty around the decision to adopt the intervention is assessed using nonparametric bootstrap re-sampling. Bootstrapping is an efficient method for calculating the confidence limits for the ICER as its validity does not depend on any specific form of underlying distribution. We perform the bootstrap to produce 5,000 replications and construct the cost-effectiveness plane based on the bootstrapping results. Costeffectiveness acceptability curves (CEAC) will be constructed based on the bootstrap iterations(55) to illustrate the probability that the surgery is more cost-effective than sling immobilisation at different acceptable ICER threshold values. The probability that surgery is more cost-effective than sling immobilisation will be marked specifically at the NICE maximum acceptable ICER threshold range of £20,000 to £30,000/QALY and also £13,000/QALY by empirical studies.(49, 56)

A range of sensitivity analyses is undertaken to assess the impact of missing data. In the main analysis, missing data will be imputed using multiple imputation method and analysed following Rubin's rule.(57) As part of the sensitivity analysis, we will conduct an additional set of analyses using the complete case analysis (CCA), whereby results are analysed only for those participants who had both the completed cost and outcome data at the same time. We will also examine the assumption of missing data pattern using pattern mixture modelling.(58) Given the implication of the painful shoulder for the patient in terms of loss of earnings, as well as private care costs, a sensitivity analysis from a broader perspective will also be conducted.

We will maintain the integrity and neutrality of the heath economic analysis by presenting a detailed *a priori* health economics analysis plan. The plan will pre-specify the methods used for the health economic analysis, the data-sources and the outcomes for analysis.

# 8 **Project management**

DIDACT will be sponsored by University Hospitals of Leicester NHS Trust. Each site will have a site PI who will be responsible locally for the study and an API who will be a trainee surgeon. The day-to-day running of the project will be undertaken by the Trial Manager based at YTU, supported by YTU senior staff. The Trial Manager at YTU will be responsible for all aspects of trial management. They will be supported by a Trial Co-ordinator, who will be responsible for the day-to-day support to trial sites, data handling, and the management of the administrative trial team. The team at YTU will meet on a weekly basis during the study and will work closely with the Chief Investigator throughout, including regular meetings to ensure that all aspects of preparation of study material, study site setup and the start of recruitment progress smoothly and throughout the trial. YTU staff will keep in close contact via email, telephone or videoconferencing throughout.

The trial team is experienced in working with local investigators at recruitment sites to ensure ethical and efficient delivery of trials in compliance with the trial protocol. In addition to regular TMGs, the trial team will keep in regular contact with sites and use joint local investigator meetings, newsletters and other forms of communication to monitor progress, support any struggling sites, and to share good practice across sites.

#### 8.1 Trial Management Group

A Trial Management Group (TMG) will monitor the day-to-day management (e.g. protocol and ethics approvals, set-up, recruitment, data collection, data management) of the study chaired by the Chief Investigator. Membership will include the Chief Investigator, coinvestigators and research staff on the project. Throughout the project there will be regular video/teleconference contact supplemented by face-to-face meetings where required. Frequency of meetings will vary depending on the stage of the trial but at least monthly during the early stages and pilot.

#### 8.2 Trial Steering and Independent Data Monitoring Committee

A Trial Steering Committee (TSC) will monitor progress of the study, provide independent advice and the independent chair will make recommendations to the funder. An Independent Data Monitoring Committee (IDMC) will monitor the data arising from the trial and recommend to the TSC on whether there are any ethical or safety reasons why the trial

should not continue. The TSC and IDMC will meet regularly to provide oversight to the study. The project will also be monitored by the sponsor and a representative will be invited to attend the TSC meetings.

# 9 Safety monitoring

Participants will be allocated to routinely delivered treatments in the NHS and therefore the risks are not increased through trial participation.

## 9.1 Definitions

Adverse events (AE) are defined as any untoward medical occurrence in a trial participant and which do not necessarily have a causal relationship with the treatment. Only medical occurrences specific to the participants' clavicle fracture that are 'unexpected' and up until the 12-month follow-up will be classified as events when non-serious. This is because 'expected' events are well known complications for the two routine treatment options which the specialist clinical care teams will be experienced in managing.

Serious adverse events (SAEs) will be defined as any untoward medical occurrence that:

- Results in death.
- Is life threatening (that is it places the participant, in the view of the Investigator, at immediate risk of death).
- Requires hospitalisation or prolongation of existing inpatients' hospitalisation (unplanned refers to emergency hospitalisations resulting in an inpatient stay; prolonged hospitalisation is deemed to be where a patient's stay is longer than expected).
- Results in persistent or significant disability or incapacity.
- Any other important medical condition which, although not included in the above, may require medical or surgical intervention to prevent one of the outcomes listed.

Medical occurrences about the participant's clavicle fracture that are serious and up until the 12 month follow-up will all be reported as SAEs (including deaths for any reason) whether expected or not.

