# 9.2 Collection, recording and reporting of adverse events

A delegated member of staff at the hospital will record all AEs or SAEs on the appropriate eCRF in REDCap. In addition, sites should follow their own local procedures for the reporting of any adverse events.

AEs and SAEs will be reported to YTU within five days or 24 hours respectively of the site investigator becoming aware of them. Once received, causality (or 'relatedness') and expectedness will be confirmed by the Chief Investigator. SAEs that are deemed to be unexpected and related to the trial treatment will be notified to the Research Ethics Committee (REC) and sponsor within 15 days.

Expected events that do not need reporting are: complications of anaesthesia or surgery (59) (e.g. wound complications, infection, damage to a nerve or blood vessel, frozen shoulder, coracoid fracture, metalwork failure and thromboembolic events) and secondary operations for or to prevent infection, malunion, non-union or for symptoms related to the metalwork.(59, 60) Nor does any of the above that may arise from sling immobilisation pathway need reporting, including swelling, bruising, discomfort or stiffness from sling use.(6, 8)

Follow-up reports a month later of all AEs and SAEs will be reviewed by the Chief Investigator to ensure that adequate action has been taken and progress made.

AEs and SAEs will be monitored regularly at TMG meetings and reported to the TSC and IDMC when they meet.

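### Sections 9.1 and 9.2 conflict on serious but expected events, so SAE reporting depends on which section a site follows

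*Protocol*

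**What the plan says.** **Protocol 9.1 (Definitions).** Expectedness works as a filter for non-serious events only. Unexpected occurrences specific to the clavicle fracture "and up until the 12-month follow-up will be classified as events when non-serious", and the reason given is that expected events are known complications which clinical teams are used to managing. Serious events are treated differently: they "will all be reported as SAEs (including deaths for any reason) whether expected or not". One seriousness criterion begins "Requires hospitalisation or prolongation of existing" and carries a bracket that explains the word *unplanned* as an emergency admission with an inpatient stay. The criterion itself does not contain that word.

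**Protocol 9.2 (Collection, recording and reporting).** Staff record all AEs and SAEs. Sites report AEs to the trials unit within five days and SAEs within 24 hours, and the Chief Investigator confirms causality and expectedness after receipt. The next paragraph opens "Expected events that do not need reporting are: complications of anaesthesia or surgery". Its examples include infection, nerve or vessel damage, "metalwork failure and thromboembolic events", and it continues with "secondary operations for or to prevent infection, malunion, non-union or for symptoms related to the metalwork". The sling arm is covered too: "Nor does any of the above that may arise from sling immobilisation pathway need reporting". The paragraph does not mention seriousness. AEs and SAEs then go to the TMG, TSC and IDMC.

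**The concern.** The two sections give different instructions for one class of event: those that are expected and also serious. Section 9.1 says report. Section 9.2, read as it stands, says there is no need. No sentence says which prevails.

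Four things are at stake for these events: the 24-hour report, the Chief Investigator's confirmation of expectedness and one-month review, the SAE tally by arm, and the AE/SAE reports on which the TSC and IDMC partly rely. An event withheld because the site judged it expected never reaches the step at which expectedness is confirmed centrally. The exemption applies to both arms, but most of the listed items arise from surgery, so any under-reporting would probably fall more on that arm.

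The stray definition of *unplanned* adds a second uncertainty. A site cannot tell whether a planned admission, for metalwork removal or for later fixation in the sling pathway, is an SAE.

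**Working it through.** The plan states no figure on this point, so the main check is a comparison of the text.

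**Step 1. Classify example events under each section.**

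| Event within 12 months | Under 9.1 | Under 9.2 |
|---|---|---|
| Expected, non-serious (e.g. stiffness from sling use) | Not an event to report | No report needed |
| Emergency inpatient readmission for deep infection | Serious (hospitalisation), so an SAE although expected | Infection is listed: no report needed |
| Thromboembolic complication of surgery needing admission | SAE, as above | Listed: no report needed |
| Planned admission for metalwork removal | Unclear: the criterion covers any hospitalisation, the bracket speaks of emergencies | Listed: no report needed |
| Planned later fixation for non-union after sling | Unclear, as above | Listed: no report needed |

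The sections agree on the first row and conflict on the second and third. On the last two rows 9.1 cannot be applied. Section 4.5.3 calls repeat surgery to remove metalwork a rehospitalisation, which points towards serious. The bracket in 9.1 points the other way.

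**Step 2. Scale, for illustration only.** Inputs: 107 participants per arm (Trial Synopsis). From the Canadian RCT cited in section 1.2, 12/27 surgical patients had a second operation for hardware removal and 6/30 sling patients had further surgery. It is an assumption that these rates apply here.

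- Surgery arm: 107 × 12/27 = 47.6, about 48.
- Sling arm: 107 × 6/30 = 21.4, about 21.
- Total: 47.6 + 21.4 = 69.0. Ratio: 47.6 / 21.4 = 2.2.
- If only 80% are followed up: 0.8 × 69.0 = 55.2, about 55.

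**Step 3. Serious share.** The protocol does not say what fraction of these operations would meet a 9.1 criterion. Taking the same fraction in both arms:

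| Share serious | Surgery | Sling | Total SAEs under 9.1 | Under 9.2 |
|---|---|---|---|---|
| 10% | 4.8 | 2.1 | about 7 | 0 |
| 25% | 11.9 | 5.4 | about 17 | 0 |
| 50% | 23.8 | 10.7 | about 34 | 0 |
| 100% | 47.6 | 21.4 | about 69 | 0 |

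The table counts secondary operations only. Other listed complications are not included.

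**The case against.** The strongest reply is that the sections can be read together. Section 9.1 is the definitions section, deals with serious expected events expressly, and uses expectedness only to explain which non-serious events are left out. Section 9.2 itself requires SAEs to be recorded and reported within 24 hours. On that reading its list is the non-serious exemption with the qualifier left off. This is plausible and may be what was meant, but 9.2 does not say it. The list follows directly after the reporting times for both AEs and SAEs, and it names items that can readily be serious. Staff working to a 24-hour limit should not have to infer the rule.

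The second reply is that the consequences are contained, and this largely stands. Section 4.5.3 collects complications in both arms at 6 weeks, 3 and 12 months, including deep infection and rehospitalisation. Under section 8.2 the IDMC monitors the data arising from the trial, not SAE forms alone. Deaths are reported whatever the cause. Notification to the ethics committee covers only unexpected related SAEs, so it is not affected.

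A reader might infer that about 48 surgical and 21 sling SAEs would go missing. The documents do not support that. The operations behind those counts are hardware removals and further surgery after sling treatment, much of it likely to be planned, which is the category whose status 9.1 leaves open. Later fixation is also described in section 4.3.1 as part of the sling pathway. The Canadian surgical arm included hook plates, which this trial excludes and which section 1.2 says need removal. Section 1.1 does use about 45% for metalwork removal when costing, so the rate is not implausible, but it remains borrowed.

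**Conclusion.** The inconsistency is in the current text and should be corrected. It affects listed events that meet a seriousness criterion in 9.1, and planned admissions that 9.1 does not classify. For these, SAE tallies, 24-hour reporting and the AE/SAE reports to the TSC and IDMC depend on which section a site applies.

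The size is not known. Secondary operations alone would give between about 7 and 69 affected events in 214 participants, assuming the Canadian rates and a serious share of 10% to 100%. The upper end needs every such operation to be serious.

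It would go too far to conclude that the IDMC cannot see these events, that the comparison of harms between arms rests on SAE counts, or that under-reporting has happened. The complication outcomes provide a separate record in both arms, and nothing in the protocol shows what sites have done. The primary DASH analysis, the sample size and the non-inferiority decision are unaffected.

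**What to change.** Reconcile 9.1 and 9.2 so that one rule covers serious expected events; the sponsor decides which. One way is to carry the line already drawn in 9.1 into 9.2: the exemption applies to expected non-serious events, and any listed event that meets a 9.1 criterion is reported as an SAE. In 9.1, state whether planned admissions count as hospitalisation, in the same words for both arms, and either use the word *unplanned* in the criterion or remove its definition. Tell sites by memo.

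A check of complication eCRFs already held, for listed events that met a seriousness criterion, is a reasonable precaution and does not imply that sites have erred.

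The cost is a protocol wording change, one memo, the optional check and somewhat more SAE forms. The outcome data and the analysis do not change.
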